15.10 Recording and Reporting of Adverse Events

The site Investigator is responsible for monitoring the safety of subjects enrolled into the study at the study sites. For this study, non-serious AEs will not be collected on the safety reporting page of the eCRF, but should be documented in the source documents and followed according to local standard of care. Events significant enough to necessitate modification of study drug dosing will be captured on the appropriate eCRF module (“Study Drug Dosing” page).

All SAEs, except for those anticipated events listed above, occurring from signed informed consent through study visit 11 will be captured on the SAE eCRF. Subjects that have screen failed will be followed for SAEs until two weeks post last study drug dose. Unless exempted as described above, all SAEs, whether or not deemed drug-related or expected, must be reported by the investigator or qualified designee within 24 hours of first becoming aware of the event. For this study, the cause of death will be reported on either the SAE or Events of interest (EVNINT) eCRF, as well as the Death eCRF page. The investigator or qualified designee will enter the required information regarding the SAE into the appropriate module of the eCRF, which will automatically result in distribution of the information to DCRI Safety Surveillance. DCRI Safety Surveillance will share all SAE reports with Novartis Pharmaceuticals. If the eCRF system is temporarily unavailable, the event, including the investigator-determined causality to study drug should be reported via the back-up paper SAE form to DCRI Safety Surveillance. Upon return of the availability of the electronic data capture (EDC) system, the SAE information must be entered into the eCRF.

Any misuse or abuse of the study drug, other medication errors and uses outside of what is foreseen in the protocol (irrespective of whether a clinical event has occurred) must also be reported to DCRI.

15.11 Follow-up of Adverse Events

When additional relevant information becomes available, the Investigator will record follow-up information according to the same process used for reporting the initial event as described above. The Investigator will follow all reportable events until resolution, stabilization or the event is otherwise explained.

DCRI Safety Surveillance will follow all SAEs until resolution, stabilization, until otherwise explained or until the subject completes the final follow-up, whichever occurs first. Investigators are also responsible for promptly reporting AEs to their reviewing IRB/EC in accordance with local requirements. The Data Safety Monitoring Board (DSMB) will review detailed safety data approximately every 3 months throughout the study.

15.12 Suspected Unexpected Serious Adverse Reaction

AEs that meet the criteria of serious, related to study drug, and unexpected per PPI, qualify for expedited reporting to the regulatory authorities. The site Investigator will assess all SAE's occurring at his/her site and evaluate for "unexpectedness" and relationship to study drug. The site Investigator is required to complete and submit a voluntary MedWatch Report for events confirmed by DCRI Safety Medical Monitor, as serious, study drug related and unexpected at: <https://www.accessdata.fda.gov/scripts/medwatch/>.

A copy of this report should be kept at the site and also forwarded to the DCRI Coordinating Center and to DCRI Safety Surveillance.

15.13 Pregnancy

Pregnancy occurring during a clinical investigation, although not considered a serious adverse event, must be reported to DCRI within the same timelines as a serious adverse event. The pregnancy will be recorded on the appropriate paper pregnancy tracking form. The pregnancy will be followed until final outcome. Any associated AEs or SAEs that occur to the mother or fetus will be recorded in the AE/SAE eCRF, within the EDC system. The pregnancy outcome of a female partner to a male study participant will not be followed. DCRI will share all pregnancy reports with Novartis Pharmaceuticals.

16 STATISTICAL METHODS AND DATA ANALYSIS

16.1 General Design Issues

All planned analyses will be prospectively defined for this study and approved by the CC prior to unblinding of data. The statistical analysis plan (SAP) will contain detailed information regarding the data analysis. The SAP will be finalized prior to trial completion and will be approved by the coordinating center statistical team as well as the National Heart, Lung, and Blood Institute (NHLBI) program officer.

Analysis of the LIFE Study will be based on intention to treat (ITT). That is, subjects will be analyzed (and endpoints attributed) according to the treatment strategy to which subjects are randomized, regardless of subsequent additional post-randomization treatment and medical care. The ITT population will correspond to all randomized subjects.

Statistical comparisons will be performed using two-sided significance tests. Baseline demographic and clinical variables will be summarized for each randomized arm of the study. Descriptive summaries of the distribution of continuous variables will be presented in terms of percentiles (e.g., median, 25th and 75th percentiles) along with means and standard deviations. Categorical variables will be summarized in terms of frequencies and percentages.

In addition, exploratory analyses will be performed to help explain and understand findings

observed from the planned analyses. Statistical tests with a 2-sided p-value <0.05 will be considered statistically significant, unless otherwise stated. Analyses will be performed using SAS software (SAS Institute, Inc, Cary, NC).

16.2 Sample Size Justification and Randomization

Subjects will be randomized in a 1:1 allocation ratio using a permuted block design with stratification based on the clinical center and atrial fibrillation status. We plan to randomize 400 subjects with planned follow-up of 26 weeks. The primary efficacy endpoint is the proportional change from baseline in the AUC for NT-proBNP levels measured at 2, 4, 8, 12 and 24 weeks.

Based on recent Heart Failure Clinical Research Network (HFN) trials with similar follow-up requirements, we are anticipating a dropout / withdrawal of consent rate of approximately 5%. However, due to deaths and other sample collection issues we anticipate as many as 20-25% of subjects will not have NT-proBNP data at the week 24 assessment.

For the primary analysis, the AUC data will be log transformed and subjects missing the NT-proBNP data at the week 24 assessment will be assigned the last observation carried forward (LOCF). Based on a 2-sample t-test with type I error of 0.05 two-sided, the total sample size of 400 randomized subjects will provide 80% and 90% power to detect a differences of 19% and 21% for LCZ696 compared to valsartan. The PARAMOUNT phase II clinical trial observed a 23% greater reduction in NT-proBNP for LCZ696 compared to valsartan at 12 weeks post-randomization in patient population with HFpEF. ⁶ The HF Network investigators believe a 20% reduction in NT-proBNP would be considered a clinically significant improvement, and this level of change falls within a range considered clinically meaningful in a recent comparative effectiveness review published by AHRQ. ⁷

Sensitivity analyses will examine the influence of the imputation for the informatively missing data. For the complete case analysis, the total sample size of 400 subjects will provide approximately 80% and 95% power to detect reductions of 20% and 25% for LCZ696 compared to valsartan, respectively. These calculations were based on a two-sample t-test and assume that the standard deviation of the log-transformed 180-day AUC measure is 0.70. ⁸

Another secondary analysis of the AUC data for NT-proBNP will be conducted using a Wilcoxon nonparametric test with a worst-rank imputation based on the time-to-death. ⁹ A sample size of 190 subjects per group with available data will provide 80% power to detect the probability of 0.58 that an LCZ696 subject will have a better response than a valsartan subject. Similarly the sample size will provide 90% power to detect the probability of 0.60 that an LCZ696 subject will have a better response than a valsartan subject.

For the composite endpoint of all-cause mortality or first HF re-admission, we anticipate a 40% event rate at 24-weeks in the valsartan arm. The total sample size of 400 subjects will provide approximately 88% power to detect a difference of 40% vs. 25% for the LCZ696 arm. Similarly, there will be 55% power to detect a difference of 40% vs. 30%. The calculations were performed

using nQuery 7.0 and assume a 0.05 type I error rate (two-sided) with 1:1 randomization.

16.3 Interim Analyses and Safety Reviews

Interim examinations of key safety and process data will be performed at regular intervals during the course of the trial. It is anticipated that the DSMB will review the accumulating data at predetermined intervals (approximately every 3 months). In addition, a summary of clinical events and adverse events will be sent to the Chair of the DSMB monthly for review. The DSMB will receive a full report 4 times each year and the Chair can call a meeting of the full DSMB at any time. The CC will create regular reports to track subject enrollment reports, rates of adherence with the assigned treatment strategy, and frequency of protocol violations. Prior to each meeting, the CC will conduct any requested statistical analyses and prepare a summary report along with the following information: subject enrollment reports, rates of adherence with the assigned treatment, and description of SAEs. The DSMB will review data masked by study group (such as X vs. Y). An interim review will be conducted using the first 200 patients randomized with analysis starting after the last of the 200 patients complete study follow-up.

16.4 Analysis of the Primary Endpoint

A general linear model will be used to estimate and statistically compare the log-transformed AUCs in the NT-proBNP values between the two treatment groups. Each individual will have one response based on the log of the proportional change from baseline in the AUC from the 2, 4, 8, 12, and 24 week measurements. Missing data for the NT-proBNP assessment at week 24 will be assigned the last observation carried forward (LOCF). The treatment effect will be summarized using a point estimate and 95% confidence interval.

Sensitivity analyses will examine the influence of the imputation for the informatively missing data and the possibility for outliers due to clinical changes including atrial fibrillation status. For a set of analyses, missing data for the NT-proBNP assessment at week 24 will be assigned a value corresponding to 2.5 and 5 times the baseline NT-proBNP value. The linear models will include covariates for the treatment group indicator variable, log of the baseline NT-proBNP, and atrial fibrillation status. A complete case analysis will be conducted to examine the sensitivity of the overall findings to the imputation algorithm. A nonparametric sensitivity analysis will compare the AUC data for NT-proBNP using a Wilcoxon test with a worst-rank imputation based on the time-to-death.⁹

16.5 Analysis of Secondary, Tertiary and Exploratory Endpoints

The key secondary endpoint, *days alive and out of hospital at 6 months, not listed for transplant (status 1A, 1B or 1-4) or undergoing transplant, implanted with an LVAD, maintained or started on continuous inotropic therapy for ≥ 7 days, or has had two hospital admissions for HF (other than the index admission*)*, will be analyzed using a regression model with indicator variables for the treatment assignment and atrial fibrillation at enrollment. For time-to-event endpoints, the

Cox regression model for survival data will be used to test the statistical significance of differences in mortality between the treatments. Kaplan-Meier curves will be generated to graphically display the mortality rates as a function of time from randomization in each treatment. Continuous endpoint data will be modelled using general linear models. Mixed models will be used for the analysis of longitudinal data. The unmatched win ratio approach of Pocock et al. will be used to analyze the modified composite endpoints.¹¹

17 DATA MANAGEMENT PROCEDURES

17.1 Overview of Data Management

The CC will have primary responsibility for data management, including the development of data collection systems, data monitoring processes, and data storage and back-up. State-of-the-art technology will be used for the management of the network's data.

17.2 Data Security

Access to databases will be controlled centrally by the CC through user passwords linked to appropriate privileges. This protects the data from unauthorized changes and inadvertent loss or damage. Database and web servers will be secured by a firewall and through controlled physical access. Database back-up will be performed daily using standard procedures in place at the CC. All disk drives that provide network services, and all user computers, will be protected using virus-scanning software.

17.3 Publication Policy

Dissemination of preliminary information can adversely affect the objectivity of study data. For this reason, investigators will not be allowed to perform subset analyses at any point before the conclusion of the study, and any data, other than safety data, cannot be used for publication or reporting outside of this study until the study is completed or discontinued by the DSMB or HFN Steering Committee.

18 STUDY ADMINISTRATION

18.1 Data and Safety Monitoring Board

A DSMB has been appointed by the NHLBI for the HFN, and will function as the DSMB for this trial. This committee consists of a group of highly experienced individuals with extensive pertinent expertise in HF and clinical trials. The DSMB will advise the HFN Steering Committee regarding the continuing safety of current subjects and those yet to be recruited, as well as the continuing validity and scientific merit of the trial. Safety data, summarized at the treatment level, will be assessed approximately every 3 months by the DSMB. The safety analyses will be based on the entire ITT population. Safety will be evaluated by comparing the occurrence of AEs and changes in laboratory values of the active treatment arm compared to the active

control arm.

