7 STUDY DESIGN

7.1 Screening / Baseline

Subjects will have an initial screening evaluation, including baseline laboratory tests as well as an assessment of LV ejection fraction, at which time preliminary subject eligibility will be determined. The LV ejection fraction may have been obtained within the prior 12 months by 2-D echocardiogram, LV angiogram or radionuclide scintigraphy. Willing subjects meeting entry criteria will be consented. Those who meet all entry criteria and are interested in study participation will be enrolled.

Enrolled subjects will complete baseline assessments and undergo a run-in period of 3-7 days with LCZ696 50 mg (equivalent to Entresto™ 24/26 mg) po BID prior to randomization. For subjects taking an ACEI, the ACEI will be withheld for ≥ 36 hours prior to first dose of LCZ696.

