7.2 Randomization Phase

This will be a 2-arm randomized, double-blind, controlled trial with an active treatment arm (valsartan).

Subjects who tolerate the run-in period with LCZ696 will be randomized 1:1 to LCZ696 or valsartan. Subjects will be randomized using procedures determined by the Coordinating Center

(CC) to one of the two treatment groups.

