10.4 Dosing Guidelines

The study will begin with a 3-7 day run-in period in which all subjects will be administered LCZ696 50 mg po BID. For those subjects taking ACEI prior to the run-in period, the first dose of LCZ696 will be withheld ≥ 36 hours after last ACEI dose. After stopping LCZ696, a 36 hour washout period is required before resuming an ACEI.

Subjects tolerating the LCZ696 in the run-in period will be randomized to either LCZ696 or valsartan. Doses will be assigned in the following fashion:

If previously taking no ACEI/ARB, low-dose ACEI/ARB[†], or eGFR < 30 ml/min/1.73m², ensure ACEI has been discontinued and the last dose was ≥ 36 hours ago, then

- LCZ696 50 mg plus placebo po BID or valsartan 40 mg plus placebo po BID

If previously taking greater than low dose ARB[†]

- LCZ696 100 mg plus placebo po BID or valsartan 80 mg plus placebo po BID*

If previously taking greater than low dose ACEI[†], ensure ACEI was discontinued and the last dose was \geq 36 hours ago, then

- LCZ696 100 mg plus placebo po BID or valsartan 80 mg plus placebo po BID*

* At Investigator discretion, study drug may be started at the low dose (LCZ696/placebo 50 mg po BID or valsartan/placebo 40 mg po BID) if there are any concerns regarding tolerability at the 100 mg / 80 mg dose.

Two weeks after randomization, upward dose titration will occur among subjects tolerating their current dose (SBP > 90 mmHg, creatinine (Cr) \leq 2.0 mg/dL, and no symptoms of hypotension). This will consist of doubling the dose up to a maximum dose LCZ696 200 mg po BID (two 100 mg tablets plus 2 placebo tablets po BID) or valsartan 160 mg po BID (two 80 mg tablets and 2 placebo tablets po BID). For those not tolerating the current dose of study drug, the dose will be down-titrated to the previous tolerated dose.

Two weeks after the prior dose titration visit and four weeks after randomization, further dose titration will occur among subjects tolerating their current dose (SBP > 90 mmHg, Cr \leq 2.0 mg/dL, and no symptoms of hypotension). This will consist of doubling the dose up to a maximum dose LCZ696 200 mg po BID or valsartan 160 mg po BID. For those not tolerating the current dose of study drug, the dose will be down-titrated to the previous tolerated dose. The total duration of study drug treatment will be 24 weeks.

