### **13. Safety analysis**

#### **13.1 – Safety Endpoint #1**

Safety Endpoint #1: Comparison of serious adverse events at the level of MedDRA preferred term, using the pre-COVID-19 population.

Response Variable Definitions: The number of patients experiencing each unique serious adverse event (SAE) type based on MedDRA preferred term within body system.

Additional Covariates: None

Handling of Dropouts and Missing Data: No adjustments for missing data will be made.

Sensitivity Analysis: Re-calculate the endpoint analysis using the original ITT population.

Statistical Tests: Fisher's mid-p will be calculated for each serious adverse event based upon the unique MedDRA preferred term within a body system.

Interpretation of Results: Lower event rates indicate a better outcome for LCZ696 arm versus Valsartan.

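### Every enrolled subject takes open-label LCZ696 in the run-in, but no planned safety analysis or final table reports those who are not then randomised

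*Protocol*

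**What the plan says.** **Exposure before randomisation.** Protocol 10.4 states: "The study will begin with a 3-7 day run-in period in which all subjects will be administered LCZ696 50 mg po BID". Protocol 7.2 then selects on tolerance: "Subjects who tolerate the run-in period with LCZ696 will be randomized 1:1 to LCZ696 or valsartan".

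**Population for the safety analyses.** Protocol 18.1 (Data and Safety Monitoring Board) states: "The safety analyses will be based on the entire ITT population". Protocol 16.1 defines the term: "The ITT population will correspond to all randomized subjects". The next sentence of 18.1 describes the evaluation as a comparison of the LCZ696 arm with the valsartan arm.

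**Final safety table.** SAP 13.1 has one safety endpoint: "Comparison of serious adverse events at the level of MedDRA preferred term, using the pre-COVID-19 population". The ITT population is its sensitivity analysis. SAP 3 gives 365 randomised patients, of whom 335 are in the pre-COVID-19 population.

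**Tolerability.** SAP 10.3 to 10.5 count symptomatic hypotension, worsening renal function and hyperkalaemia between randomisation and the Week 24 assessment.

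**Collection.** Protocol 15.10 captures SAEs from signed consent and adds: "Subjects that have screen failed will be followed for SAEs until two weeks post last study drug dose". Protocol 12.1 and Appendix A require a contact with run-in failures about two weeks after their last dose.

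**The concern.** The run-in is the first exposure to LCZ696 in this trial's population. A subject who has an SAE on those doses and is not randomised belongs to no treatment arm, and so to neither of the populations named for the safety analyses. The event is recorded, but no planned count, listing or table shows it.

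This matters more here than in most run-in designs. Protocol 11.6 says that the risks and benefits of LCZ696 in advanced heart failure with lower blood pressure are unknown, and gives this as the reason for the trial. Protocol 6 notes that only 33 class IV patients were assigned LCZ696 in the earlier large outcome trial. A safety report that starts at randomisation describes only patients who had already tolerated the drug for several days. Without the number who entered the run-in and what happened to those who left, a reader cannot place the randomised results in context.

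**Working it through.** **Step 1. Follow one run-in failure through the plan.**

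| Place | Who or what is covered | Run-in failure included? |
|---|---|---|
| Protocol 7.1, 10.4 | All enrolled subjects take LCZ696 | Yes, exposed |
| Protocol 15.10 | SAEs from consent; screen failures to two weeks after last dose | Yes, collected |
| Protocol 18.1 with 16.1 | All randomised subjects, compared by arm | No |
| SAP 13.1, main analysis | Pre-COVID-19 population | No |
| SAP 13.1, sensitivity analysis | ITT population | No |
| SAP 10.3 to 10.5 | Events from randomisation onward | No |
| Protocol 15.11, 16.3 (DSMB reviews) | Population not stated | Unknown |

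Neither document defines an enrolled, run-in or all-exposed safety population, or plans a summary of run-in failures.

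**Step 2. Check that both SAP populations contain randomised patients only.** SAP 3 gives 335 patients in the pre-COVID-19 population and 30 who contribute only to the sensitivity analyses. 335 + 30 = 365, the stated randomised total. The main SAE table therefore also leaves out 30/365 = 8.2% of randomised patients, and only the sensitivity analysis meets the ITT rule in Protocol 18.1.

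**Step 3. Illustrate the number affected.** The documents give neither the number entering the run-in nor the proportion not randomised. Let f be an assumed proportion not randomised and N the number randomised. Then:

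- Number not randomised = N/(1 - f) - N.
- Share of exposed subjects in the ITT table = 1 - f.
- Share in the main SAE table = (335/365) × (1 - f).

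| Assumed f | Not randomised, N = 365 | Not randomised, N = 400 (planned) | ITT table covers | Main SAE table covers |
|---|---|---|---|---|
| 5% | 19 | 21 | 95% | 87.2% |
| 10% | 41 | 44 | 90% | 82.6% |
| 15% | 64 | 71 | 85% | 78.0% |
| 20% | 91 | 100 | 80% | 73.4% |

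Example at 10%: 365/0.90 = 405.6, and 405.6 - 365 = 40.6, or about 41. These are counts of subjects, not of events.

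**Step 4. Check the start date of the by-arm table.** SAEs are captured from consent (Protocol 15.10), and SAP 13.1 sets no earliest onset date. As written, an SAE during the LCZ696 run-in, in a subject later randomised to valsartan, could be counted under valsartan.

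**The case against.** The case on the other side has several parts, and most of it stands as a limit on the point.

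- **Run-in failures do not belong in the between-arm comparison.** This is correct. They have no arm, and their absence from that comparison is sound design. The point is that nothing else reports them.
- **The DSMB may see these events.** A reader might infer from Protocol 18.1 that the board is blind to run-in harm. The documents do not support that. Protocol 15.11 gives it detailed safety data about every three months. Protocol 16.3 adds a description of SAEs before each meeting and a monthly event summary to the Chair. None of these states a population, so run-in events are neither assured nor excluded.
- **Some of the most important events are missing for another reason.** A reader might infer that angioedema, sudden cardiac death or symptomatic hypotension is lost because of the run-in. Protocol 15.9 sends these to the Events of Interest page and not to AE/SAE capture, so they are outside the SAE table for randomised patients too. For them the run-in exclusion is a second reason.
- **The lack of a safety trigger is not specific to the run-in.** SAP 14 says there were no pre-specified safety stopping guidelines for the trial as a whole.
- **Not every non-randomised subject is intolerant.** Appendix A rechecks eligibility at the randomisation visit, and consent can be withdrawn.
- **Individual cases are handled.** SAEs that are not exempt are reported within 24 hours (Protocol 15.10), and serious, related, unexpected events go to the regulator (15.12). This protects case reporting but gives no denominator and no place in the final report.

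**Conclusion.** The gap is real and limited to analysis and reporting. The safety analyses that the documents specify contain randomised subjects only, and the tolerability events are counted only from randomisation. SAEs of run-in failures are collected, but no planned analysis or final table reports them. The trial's account of LCZ696 safety in advanced heart failure is incomplete at the first exposure.

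This conclusion rests on the population definitions and needs no assumed rate. The size does need one: about 19 to 91 subjects for 365 randomised, if 5% to 20% of those entering the run-in were not randomised. The documents neither support nor exclude that range, and it says nothing about how many events are involved.

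The documents do not show that the DSMB was uninformed, that collection failed, or that the randomised comparison should have a different population. The missing onset date in SAP 13.1 is a separate, smaller weakness with the same source.

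**What to change.** In Protocol 18.1 and SAP 13:

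1. Keep the between-arm safety comparison on randomised subjects.
2. Define a descriptive run-in safety population: all subjects who took at least one open-label LCZ696 dose.
3. For it, report the number entering, the number not randomised (with reasons where recorded), and deaths, SAEs and recorded events of interest. Count from the first run-in dose to randomisation, or to two weeks after the last dose for subjects not randomised.
4. State that DSMB reports include this table while reviews continue, and put it in the final safety report. The SAP already reports 365 randomised and describes the DSMB reviews in the past tense, so at that stage only the final table may still be possible.
5. Limit the by-arm SAE table in SAP 13.1 to events with onset after randomisation, and show run-in SAEs in the new table.

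The cost is some wording and one additional descriptive table. It changes no dose, schedule, clinical rule, significance level or sample size. For subjects who screen fail, Protocol 15.10 promises follow-up for SAEs only. If events of interest or reasons for not being randomised were not recorded for them, the table is limited to disposition, deaths and SAEs, and should say so.
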